6.0 Number of Subjects

275

7.0 Setting

The MUSC Renal Transplant clinic is located on the 9th floor of the Rutledge Tower. The RT recipients at the Ralph H. Johnson VA Medical Center are followed at the Nephrology outpatient clinics on the first floor. Nephrologists, physician assistants, pharmacists and nursing personnel are present at both facilities. These individuals are well trained in the administration of vaccines.

The study and consent and HIPAA forms will be explained to the potential participant by the study staff in a private room

Blood draws will be performed by staff trained in phlebotomy or phlebotomists at the facility laboratories. The group 5, healthy volunteers, 35-45 years of age will be asked to come to the P.I.'s laboratory at the Strom Thurmond Building Room 411 and study, consent and HIPAA explained in private by the study personnel. Either PPV23 or PCV13 will be administered by [name]. Blood samples will be obtained at the MUSC laboratory.

Study Sites

1. The MUSC Renal Transplant clinic is located on the 9th floor of the Rutledge Tower
2. The nephrology clinic at the Ralph H. Johnson VA Medical Center
3. the P.I.'s laboratory at the Strom Thurmond Building Room 411

8.0 Recruitment Methods

- Potential study participants will be recruited from Ralph H. Johnson Veterans Affairs Medical Center and Medical University of South Carolina during the appointment with their treating physician. Flyers will be posted in the waiting room areas of the clinics and attending physicians and clinic nurses will be asked to keep this study in mind and mention availability of these studies to their patients when ordering PCV13 for them.
- Potential study subjects will be explained the purpose of the study and how their information was obtained (from a treating physician or a chart review); further the eligibility criteria will be explained and what involves in participating in the study: procedures, estimated time of commitment, any reasonably foreseeable risks, benefits, and compensation. In a similar manner, healthy volunteers will be recruited through flyer advertisement on MUSC campus as well as in VA.
- Potential study subjects will be identified by reviewing medical records and by physician's recommendations.
- Flyers will be used to recruit study subjects as well as broadcast emails for MUSC and VA employees and volunteers.

9.0 Consent Process

Informed Consent will be obtained in a private room from all participants at either:

1. The MUSC Renal Transplant clinic is located on the 9th floor of the Rutledge Tower
- Or 2. The nephrology clinic at the Ralph H. Johnson VA Medical Center
- Or 3. the P.I.'s laboratory at the Strom Thurmond Building Room 411

Consent will be sought of **competent adults** who express interest in the study. The purpose of the study, the study details regarding gathering health information and obtaining blood samples, the potential benefit and risks involved, including risk of blood draw and vaccination, will be explained in detail and in layman terms, as well as the non-standard of care explained to the potential subject (i.e. blood draws for groups 1-4, vaccination protocol and blood draws for group 5). The subject will be encouraged to ask questions and they will be asked to answer questions regarding essential parts of the study to ensure proper understanding of the study requirements. We will explicitly explain that the study is completely voluntary, and they can withdraw from the study at any time. Additionally we will explain that participation is independent of the medical care the subject receives at the Ralph H Johnson VA medical center or MUSC.

Consent will be obtained as described above in the presence of the P.I. or study coordinator. The potential volunteer will be given written information, and opportunity for questions will be provided. Volunteers will be questioned concerning the study to assure complete understanding.

The consent will only be obtained from the participant him or herself and not from a surrogate.

There will be no waiting period between consent and beginning of the study

The study and consent form will be reviewed in depth and after each separate section the participant will be asked to summarize the section in his or her own words to ensure understanding.

Vulnerable populations, i.e. employees at the P.I.'s institution will be recruited, however they will **ONLY** be recruited if they have

1. no personal relationship with the PI
- 2 are not directly employees of the PI or a division where they could be vulnerable to coercion or undue influence.

3. it will be made clear to all these participants that participation is strictly voluntary

4. recruitment will only be performed in an in personal mass email

10.0 Study Design / Methods

The overall objective of this proposal is to characterize the immune response and explore possible mechanisms of poor vaccine responsiveness following immunization with PCV in the rapidly growing group of elderly with RT. As the RT population is a heterogeneous group we will study only those in whom the underlying cause of renal failure is diabetes mellitus type 2 (DM2) and/or hypertension (HTN). There will be 5 study groups as outlined above.

Volunteers from all 5 study groups will be recruited as above. All individuals from study groups 1-4 who meet the study criteria will receive Prevnar13[®] on day 0. Group 5 volunteers will be recruited during the first year of the study and those who have not previously received PPV23 will receive PPV23 on day 0 and PCV13 on day 366. Blood samples will be obtained as outlined below and results obtained in various groups will be compared.

Timing of blood samples

Peripheral blood samples will be collected at day 0 (pre-immune), day 7, and day 30 (4 weeks post-PPV23) for groups 1-4 and at days 366, 373 and 396 for group 5. In addition, day 5, and 10 blood samples will be obtained from a limited (n=10) number of elderly RT participants to determine the optimal time point for circulation of PPS-specific B cells. Yearly blood samples will be obtained thereafter for serum antibody and OPA analyses to test longevity of antibody and OPA responses. Samples from days 0, 30 and yearly samples will be used for antibody titers and opsonophagocytic assays. Samples from day 0 (day of vaccination with PCV13) and day 7 will be used for flow cytometric analysis. The day 7 time point for isolation of antigen-specific B cells was specifically chosen as we have extensively studied temporal dynamics of antigen-specific B cell in peripheral blood samples (unpublished studies) and have found that the highest number of antigen-specific B cells are present in the peripheral circulation at day 6 and 7 with rapid (70+%) decline at day 8 in healthy young, elderly including those with DM2 and HTN, and HIV-positive. At day 30, a minimal number of PPS-specific B cells were present. Others have described similar findings [28, 29].

However, it is possible that day 7 may not be the optimal time point for the isolation of antigen-specific B cells in the RT populations. Therefore, we will obtain blood samples on days 5, 7, and 10 from the first 10 participants in the aging RT group to redefine optimal time point for antigen-specific B cell isolation in this population. The first 10 participants in Group 1 will be recruited from both MUSC and the VAMC. The optimal time point will be applied to **all** subsequent RT participants.

BAFF concentration will be measured at day 0.

All groups: All recruited subjects will agree to be tested for HIV by rapid HIV test, HBsAg and HCV if their status is not available in their health records. In addition they will agree to have CBC and Complete metabolic profile (CMP) and hemoglobin A 1c (HbA1c) should a recent (<6 months old) result not be available.

Groups 1-4

All individuals in groups 1-4 agree to

1. Receive PCV13 (Prevnar[®]13): this is STANDARD of care in all group 3 recruited and enrolled subjects

2. Experimental part of the protocol they will agree to:

In the first 10 vaccine recipients in groups 1 : donate blood specimens: at 7 different times of up to 60 mL per visit: day 0, day of vaccination: at day 5, day 7, day 10 and at day 30 and yearly

thereafter up to 2 years. Samples drawn at days 5, 7 and 10 are used to determine the optimal time point of isolation of PPS-specific B cells.

Participants 11-40 in group 1 and all Group 2: will donate blood samples at 5 different time points of up to 60 mL per visit: day 0, day of vaccination: at optimal time point being **either** day 5 **or** day 7 **or** day 10 and at day 30 and yearly thereafter up to 2 years.

The optimal time point of isolation of PPS-specific B cells post-vaccination in both young and elderly healthy and diabetic populations had been determined by us in previous studies, however this may vary in the transplant population. We will therefore test this in the first 10 RT subjects enrolled in both groups 1 and 2. The first 10 participants in Group 1 will be recruited from both MUSC and the VAMC.

Groups 3 and 4: There will be 5 visits: blood draws of up to 60 mL per visit: day 0, day of vaccination: at day 7 and at day 30 and yearly thereafter up to 2 years.

Group 5

1. Receive PPV23 (Pneumovax®) on day 0 of enrollment if they have never received PPV23. This is to assure that all participants in the study have been immunized with PPV23 at least 1 year prior to receiving PCV13.

2. Receive PCV13 (Prevnar®13) on day 366

2. Experimental part of the protocol they will agree to:

All vaccine recipients donate blood samples up to 60mL per visit: at 5 different times: day 366 day 373, 396 and yearly thereafter up to 3 years, i.e. referred to years 1, 2 and 3.

In group 5, healthy 35-45 year olds, PPV23 and PCV 13 may not be routine part of care (in those without any underlying disease or tobacco use) and vaccination with PCV13/PPV23 is not part of routine care in any of these individuals, **however neither vaccination regimen is contra-indicated in these age groups and is NOT associated with a higher rate of adverse events exceeding vaccination in other age groups.** In fact, significant benefit may be derived from either vaccine regimen.

Visit #	Experimental part of protocol	Standard of care action	Time commitment
1	Enrollment Blood draw	PCV13	60 min
2-6 or 7	Report side effects Blood draw	-	30 min

Table 1. Groups 1-4. First 10-12 subjects enrolled

Visit #	Experimental part of protocol	Standard of care action	Time commitment
1	Enrollment Blood draw	PCV13	60 min
2-4 or 5	Report side effects Blood draw	-	30 min

Table 2. Groups 1 Subjects 11-55 enrolled and all of Group 2,3 and 4

Visit #	Experimental part of protocol	Standard of care action	Time commitment
---------	-------------------------------	-------------------------	-----------------

1	Enrollment PPV23	-	60 min
2	PCV13 Blood draw	-	40 min
3-6 or 7	Report side effects Blood draw	-	30 min

Table 3. Group 5. All enrolled unless previously vaccinated with PPV23 in which case PPV23 will not be administered and enrollment will take place at “visit 2” with time commitment of 60 minutes.

The vaccine(s) administered to the participants are FDA approved vaccinations and vaccination protocols. The standard and recommended dose of vaccine will be administered either by a qualified nurse or physician and both vaccines are considered low risk. In groups 1-4 PCV13 will be administered per standard of care and is not part of the experimental protocol. In group 5, both PPV23 and PCV 13 are not routine part of care and are part of the experimental protocol. These vaccines have however been extensively studied in this and other populations and are considered low risk and 70-80% protective against pneumococcal disease [30].

The risk associated with blood draws is minimal.

The data to be collected will be stored using an excel spread sheet. The data include:

-cause of end stage kidney disease if applicable

Date of kidney transplant

Complete blood count (CBC), comprehensive chemistry profile including renal and liver functions, HbA1c, serum albumin as measure of nutrition, HbsAg, HCV and HIV test

Pre- and post-immunization serum antibody titers and opsonophagocytic antibody titers to PPS14, 19A and 23F in ug/mL

IgM and switched memory B cell number and percentage

PPS+ B cell number and percentage

Serum BAFF concentration

Gene expression of the genes listed below in Table 4

#	GENE SYMBOL	GENE TITLE	PROTEIN FUNCTION	#	GENE SYMBOL	GENE TITLE	PROTEIN FUNCTION
Apoptosis				Lymphocyte signaling			
1	Bcl-2	B-cell lymphoma 2	Apoptotic suppressor	30	CBLB	E3 ubiquitin-protein ligase	Negatively regulates B cell Ag receptor signaling
2	Bcl-Xl (BCL1)	B-cell lymphoma-extra large	Apoptotic suppressor	31	FCRL2	Fc receptor like 2	Expressed in memory B cells in humans
3	Mcl-1	Induced myeloid leukemia cell differentiation protein Mcl-1	Apoptotic suppressor	32	CD1D	CD1D	Antigen presentation
4	BAX	BCL2-associated X protein	Pro-apoptotic function	33	CD200	OX2 membrane glycoprotein	Controls inflammation; immunosuppression
5	BAD	BCL2-associated agonist of cell death	Pro-apoptotic function	34	LAIR1	Leukocyte associated immunoglobulin like receptor 1	Inhibitor of B cell mediated signaling
6	BIM (BCL11)	BCL2-interacting mediator of cell death	Pro-apoptotic function	35	CD72	B cell differentiation antigen CD72	Negative regulator of B cell responsiveness
7	FAS	Fas cell surface death receptor	Apoptosis signaling	36	RFTN1	Raft linking protein	B cell antigen receptor mediated signaling
8	BIK	BCL2-interacting killer	Pro-apoptotic function	37	LCP2	Lymphocyte cytosolic protein 2	B cell receptor signaling
9	TNFSF15	Tumor necrosis factor alpha	Activates NFkB and MAPK, promotes activation of caspases and apoptosis	38	GCET2 (GCSAM)	Germinal center associated signaling and motility	B cell signaling and motility
10	Siva1	Siva 1 apoptosis inducing factor	CD27 binding protein, pro-apoptotic	39	CD38	CD38 molecule	Signal transduction
Cytokines and receptors				40	NT5E	5' nucleotidase ecto	CD73; promotes class switching exonucleases
11	IL-1B	Interleukin1beta	Inflammatory mediator, plays a role in cell differentiation, proliferation and apoptosis	41	CD39	CD39 molecule	Exonucleases
12	IL-6	Interleukin 6	Inflammation and maturation of B cells	42	MS4A1	Membrane spanning 4-domain A1	Plays a role in T cell independent immune response
13	IL-7	Interleukin 7	Plays a role in B cell development	Igs			
14	IL-8	C-X-C motif chemokine ligand	Chemokine, mediator of the inflammatory response	43	IgD	Immunoglobulin heavy constant delta	Effector phase of humoral immunity
15	IL-10	Interleukin 10	Immune regulator, inhibits certain cytokines; cell survival and proliferation	44	IgA	Immunoglobulin alpha Fc receptor	Mediates immune response to pathogens
16	IFN-gamma receptor	Interferon gamma receptor	Innate and adaptive immune response	Metabolism			
17	IFN-gamma	Interferon gamma	Innate and adaptive immune response	45	HKII	Hexokinase 2	Hexokinases phosphorylate glucose to produce glucose-6-phosphate (G6P)
18	TNF-alpha	Tumor necrosis factor alpha	B cell function	46	PFKP	Phosphofructokinase	Catalyzes conversion of fructose 6-phosphate to fructose 1,6-bisphosphate
19	TLR1	Toll like receptor 1	Innate immune response	47	ENO1	Enolase 1	Glycolytic enzyme
20	CCR2	C-C motif chemokine receptor 2	Mediates chemotaxis	48	PGAM	Phosphoglycerate mutase	Enzyme that catalyzes step 8 in glycolysis
Transcription factors				49	LDHA	Lactate dehydrogenase A	Enzyme that catalyzes the inter conversion of pyruvate and L-lactate with interconversion of NADH and NAD+
21	IRF4	Interferon regulatory factor 4	Lymphocyte specific transcriptional activator that regulates TLR signaling	51	COXII	Cytochrome c oxidase subunit 2	Component of respiratory chain
22	BACH2	BTB domain and CNC homolog 2	Transcriptional repressor, expressed through B cell differentiation; major target Blimp1=Prdm1	52	CPT1	Carnitine palmitoyltransferase 1 a	Mitochondrial oxidation gene
23	PRDM1	PR domain zinc finger protein 1	Controls plasma cell differentiation	53	GPT2	Glutamic-pyruvic transaminase	Encodes mitochondrial alanine transaminase
24	XBP1	X-box binding protein 1	Controls late events of plasma differentiation	55			
25	Bcl6	B-cell CLL/Lymphoma 6	Transcription repressor required for GC formation antibody affinity maturation	55	ACTB	Actin beta	Conserved motif, ubiquitously expressed in all eukaryotic cells
26	Pax-5	Paired box-5	TF B cell lineage specific proteins				
27	IKZF3	Zinc finger protein Icos	TF B cell proliferation and differentiation				
28	SPIB	Spl-B Transcription factor	B cell development and antigenic stimulation				
29	FOXO1	Forkhead box o1	Plays a role in b cell differentiation				

Table 4. Gene expression to be studied by single cell PCR.

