4.0 Study Endpoints (if applicable)

The primary endpoint of this study is: quantify the antibody titers in mg/mL and opsonophagocytic antibody titer calculated as serum dilution, number of polysaccharide specific B cells, and absolute number of cells/mL induced by vaccination with PCV13.

Secondary endpoint of the study is to describe differences in gene expression of 56 genes to be determined by single cell PCR and comparing these between groups.

The primary safety endpoint of the study is measured as minimal versus moderate local side effect. Minimal side effect measured as no impairment in activity. Moderate local side effect is a side effect affecting use of the extremity for less than 24 hours.

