Monitoring will be performed at each study visit by the study coordinator and/or P.I. and will occur at the Ralph H. Johnson VA Medical Center and MUSC and all AEs will be recorded on an event form with physician/nurses/coordinator notes attached. These will be reviewed by the safety monitoring committee. The safety monitoring committee will include board certified Infectious Diseases specialists. Meetings will occur on a quarterly basis. [name], the P.I. will arrange for the meetings quarterly, make all materials available for review by the committee and be ultimately responsible for the meetings.

The study endpoints will be reporting and assessing safety of the vaccination and blood draw procedures and to ensure that these procedures are well within the acceptable complication risk associated with vaccination and blood draws.

All serious, unexpected, AND related adverse events will be reported to the MUSC IRB within 10 working days of learning of the event.

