The risk of pneumococcal vaccination adverse side effects is minimal. In the rare event that an adverse reaction of greater magnitude than local reaction occurs, each volunteer is provided with a contact telephone number to reach research personnel who will see and potentially treat the adverse reaction as appropriate. The most common of these occasional adverse reactions consists of low grade fever, malaise and swollen lymph nodes, treatable with 2 days of prednisone. Adverse events associated with blood draws are rare and most commonly consist of prolonged bleeding treated with the application of local pressure.

All adverse events will be monitored and recorded. Monitoring will take place at every visit by the study coordinator and the P.I.

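### Group 5 volunteers given study PPV23 on day 0 have no scheduled contact for 366 days, so local reactions to that dose cannot be captured reliably or prospectively

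*Combined protocol and SAP*

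**What the plan says.** Section 10.0 sets the vaccine sequence for Group 5: "those who have not previously received PPV23 will receive PPV23 on day 0 and PCV13 on day 366". Its Group 5 list likewise gives PPV23 "on day 0 of enrollment if they have never received PPV23". Volunteers vaccinated with PPV23 before the study skip that dose and enrol at visit 2.

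Both vaccines are study interventions in this group. Section 3.0 lists them as two interventions, and section 10.0 states: "In group 5, both PPV23 and PCV 13 are not routine part of care and are part of the experimental protocol".

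Blood is drawn in Group 5 "at 5 different times: day 366 day 373, 396 and yearly thereafter up to 3 years". In Table 3, visit 1 is enrolment and PPV23, visit 2 is "PCV13 Blood draw", and a side-effect report first appears in the row for visits 3 to 6 or 7.

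On safety, section 4.0 says: "The primary safety endpoint of the study is measured as minimal versus moderate local side effect". Minimal means no impairment of activity. Moderate means that use of the limb is affected for under 24 hours. The sentence names no vaccine. Section 13.0 adds: "Monitoring will be performed at each study visit by the study coordinator and/or P.I", and section 15.0 repeats that monitoring takes place at every visit. Section 15.0 also gives volunteers a telephone number, for use "In the rare event that an adverse reaction of greater magnitude than local reaction occurs".

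**The concern.** PPV23 in Group 5 is given to healthy volunteers for the purposes of the study, so that every group has had PPV23 before PCV13. Section 13.0 commits the study to reporting and assessing the safety of the vaccination. Yet nothing in the detailed schedule collects local reactions to this dose near the time they happen. A reaction that impairs the arm for less than a day is not something a volunteer can be expected to grade a year later.

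At stake is the safety record for one of the two vaccines that the study itself gives to Group 5. If the record is thin because nobody asked in time, a reader of the results may take it for low reactogenicity.

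**Working it through.** The plan states no figure for this point, so there is none to reproduce. The check sets the schedule against the endpoint and then gives a rough scale.

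**Timing.** PPV23 is on day 0, and PCV13 and visit 2 are on day 366 (section 10.0). The next sampling days are 373 and 396, so visit 3 of Table 3 is day 373 and visit 4 is day 396.

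- PPV23 to the first side-effect report listed in Table 3: 373 - 0 = 373 days. By then PCV13 was given 373 - 366 = 7 days ago.
- PPV23 to the earliest enquiry under the every-visit wording of sections 13.0 and 15.0: 366 - 0 = 366 days.
- PCV13 to the listed reports in the same group: 7 days, then 396 - 366 = 30 days.
- PCV13 to the first report in Groups 1-4: Tables 1 and 2 list it from visit 2, which section 10.0 places on day 5, 7 or 10 for transplant recipients and on day 7 for Groups 3 and 4.

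**Other routes.** The telephone number in section 15.0 is for reactions greater than local, so it does not collect a local endpoint. No diary, card, call or visit shortly after PPV23 is described.

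**Scale.** Section 15.0 quotes PPV23 injection-site pain, soreness or tenderness at 60.0% and swelling or induration at 20.3%. Group size is taken as 40 (section 12.0) to 55 (275 in section 6.0 divided by 5, assuming equal groups). With s the share who are PPV23-naive, the expected count is n × s × rate.

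- s = 1 (upper limit): pain 40 × 0.600 = 24 to 55 × 0.600 = 33; swelling 40 × 0.203 = 8.1 to 55 × 0.203 = 11.2.
- s = 0.5 (illustration only): pain 12 to 16.5; swelling 4.1 to 5.6.

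The documents do not give s. The rates are also not split by effect on activity or limb use, so these are not counts of minimal or moderate events as section 4.0 defines them.

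**What timely collection would give.** With s = 1 and a true rate of 60%, the 95% half-width is 1.96 × √(0.6 × 0.4 / n). That is 15 percentage points at n = 40 and 13 at n = 55, enough for a useful description.

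**The case against.** Four arguments deserve weight.

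First, sections 13.0 and 15.0 require monitoring at every visit, and day 366 is a visit. This stands. A reader might infer from Table 3 that nobody asks about PPV23 until after PCV13, or that a reaction bearing on common exclusion 3 (known serious allergy to the pneumonia vaccine) would go unasked before the second vaccine. The documents do not support that: the general wording calls for monitoring on day 366, and Table 3 simply omits it. It also follows that the endpoint is not strictly unmeasurable. What remains is that an enquiry 366 days later is too late for a brief local reaction.

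Second, the safety endpoint may be meant for PCV13 only. The immunogenicity endpoint beside it names PCV13, PPV23 serves as a preparatory dose, and Groups 1-4 had PPV23 before the study. But section 4.0 sets no such limit, and section 3.0 counts PPV23 as an intervention. The scope is ambiguous. If PCV13 alone is meant, the experimental PPV23 dose has no defined safety endpoint.

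Third, section 3.0 lists Group 5 samples at days 0, 7 and 30, and section 14.0 calls days 7 and 30 the second and third visits. Counted from enrolment, these would be timely contacts after PPV23. Neither section says from which vaccine the days run, and the more specific schedule and Table 3 in section 10.0 contradict that reading. The conflict has to be resolved.

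Fourth, both vaccines are licensed and described as low risk, a telephone route exists for more serious reactions, and no immunogenicity comparison in section 12.0 depends on these data. All of this is true. It limits the importance of the point without supplying the missing data.

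**Conclusion.** The point holds for PPV23-naive Group 5 volunteers. As the detailed schedule stands, local reactions to their study PPV23 dose would first be asked about 366 days later under the general monitoring wording, or 373 days later under Table 3, against 5 to 10 days after PCV13 in Groups 1-4. The endpoint in section 4.0 cannot be captured reliably or prospectively for that dose.

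At most about 24-33 people with pain and 8-11 with swelling are affected. This assumes a group of 40 to 55, all PPV23-naive, and the quoted rates; a lower naive share reduces the counts in proportion. A reader might go further and predict that the trial will show almost no PPV23 reactions. That does not follow: data not collected are missing, not zero, and the risk is one of misreading.

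This should be corrected because the remedy is cheap. It does not threaten the primary immunogenicity analyses.

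**What to change.** - Reconcile Table 3 with sections 3.0, 13.0, 14.0 and 15.0. State for Group 5 from which vaccine each visit day is counted.
- State in section 4.0 whether the safety endpoint covers PPV23 as well as PCV13.
- List a side-effect report at visit 2 of Table 3, ahead of the PCV13 entry.
- Give each PPV23 recipient a one-page reaction card at visit 1 (local reaction, hours of impaired limb use, systemic symptoms), with one call or email from existing study staff at about one week.
- Report PPV23 and PCV13 reactions separately in Group 5, with the number of volunteers asked as the denominator for each.

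The cost is a wording change, a card and a small amount of coordinator time for up to about 55 volunteers. No visit or blood draw is added.
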